- ⁱ TLS monitoring test: TLS monitoring tests consists of the chemistry analytes serum potassium, phosphorous, calcium, uric acid, and creatinine and will be performed at the timepoints in the SOA. The pre-dose samples must be collected within 4 hours before AMG 176 administration to ensure electrolytes are within normal range.

 Note: The pre-dose safety chemistry and TLS monitoring tests can be drawn at the same time provided they are collected within 4 hours before AMG 176 administration.
- ^j Cardiac monitoring tests: Cardiac monitoring tests include the following analytes: troponin (I or T), creatine kinase-muscle/brain (CK-MB), and N-terminal prohormone of brain natriuretic peptide (NT-pro-BNP). These cardiac monitoring tests will be collected at the time points specified in the SOA and analyzed locally. In addition, samples will need to be submitted to the central lab. Refer to the central lab manual.
- k Pregnancy test (serum or urine). Applies to females of childbearing potential and will be performed locally at screening, prior to each treatment cycle (pre-dose), end of treatment, and at the safety follow-up visit. Additional on-treatment pregnancy testing may be performed at the investigator's discretion if there is suspicion that a female subject is pregnant or per local laws and regulations.
- ¹ HIV: to be performed only if required by local regulatory authorities.
- ^m PK: PK samples should be collected at the exact nominal time point as noted. For pre-dose PK sample, the sample should be collected within 1 hour before the dose. For all other timepoints, PK samples should be collected within ± 15 min of the designated time points. If unable to collect a PK sample at the specified nominal time point, then collect the sample as close as possible and record the actual collection time. Note: It is important to document the exact date and time of investigational product administration and PK sample collection.
- ⁿ AMG 176 PK: samples collected and analyzed for AMG 176 at the timepoints indicated. All AMG 176 timepoints are relative to start of infusion.
- o Azacitidine PK: samples collected and analyzed for azacitidine at the timepoints indicated. All azacitidine timepoints are relative to azacitidine administration.

Protocol Number: 20200392

Date: 28 April 2022 Page 27 of 149

^p Cytomorphology: bone marrow smears (slides) at screening, pre-dose on day 1 of cycle 2 and cycle 3 and thereafter prior to every other cycle or when clinically indicated until disease progression. Bone marrow biopsies/aspirates may be performed with a ± 3 day window.

- ^q EOT and SFU: In any case of premature treatment discontinuation, the investigator should make every effort to perform all examinations scheduled for the EOT and SFU visits. These data should be recorded, as they comprise an essential evaluation that should be performed prior to removing any subject from treatment and to allow for the evaluation of the study endpoints. The EOT visit will occur upon the decision to end the treatment (eg, due to intolerable AE, disease progression). The SFU visit will occur 30 days (+ 3 days) after last dose of protocol required therapies.
- Note: If a subject withdraws consent, it is important to distinguish between withdrawal of consent from treatment (partial withdrawal of consent) which will allow for continued follow-up in LTFU (eg, for survival) or withdrawal of consent from study (full consent withdrawal). These discussions should be thoroughly documented in the subject's medical records.
- LTFU/EOS: Long-term follow-up (LTFU) visits will occur every 3 months for up to 1 year after EOT. The EOS for a subject will occur when the subject completes the LTFU or dies, whichever occurs first.
- Note: If a subject withdraws consent, it is important to distinguish between withdrawal of consent from treatment which will allow for continued follow-up in LTFU (eg, for survival) or withdrawal of consent from study. These discussions should be thoroughly documented in the subject's medical records.
- ^s During the Long-term follow-up phase, serious adverse event(s) suspected to be related to Investigational Product will be reported to Amgen. After end of study serious adverse event(s) suspected to be related to Investigational Product will be reported to Amgen. Please refer to Section 8.4.6.1.3 for additional details.

Protocol Number: 20200392

Date: 28 April 2022 Page 28 of 149

2. Introduction

2.1 Study Rationale

Programmed cell death or apoptosis is a survival mechanism utilized by different types of cancer, with evasion of apoptosis leading to malignant transformation (Fouad and Aanei, 2017; Hanahan and Weinberg, 2000). The process of apoptosis is regulated by complex protein-protein interactions between subgroups of the B-cell lymphoma/leukemia 2 (BCL2) protein family (Strasser et al, 2011; Czabotar et al, 2014). Myeloid Cell Leukemia 1 (MCL1) is an anti-apoptotic member of this protein family that promotes cell survival (Kozopas et al, 1993). With apoptotic stimuli, pro-apoptotic BCL2 homology 3 (BH3)-only proteins, such as BCL2-Interacting Mediator of cell death (BIM) and p53-Upregulated Modulator of Apoptosis (PUMA), bind MCL1 and other pro-survival BCL2 family members, thus disrupting interactions between MCL1 and BAK and BAX. This disruption leads to the activation and oligomerization of BAK and BAX, Mitochondrial Outer Membrane Permeabilization (MOMP), release of cytochrome C, caspase activation, and ultimately cell death (Youle and Strasser, 2008). MCL1 is expressed in a range of human and mouse tissues (Strasser et al, 2011; Thomas et al, 2013; Wang et al, 2013), and overexpression of MCL1 has been implicated in the development of numerous solid and hematopoietic malignancies (Glaser et al, 2012; Kotschy et al, 2016; Ashkenazi et al, 2017; Merino et al, 2017), as well as in resistance to chemotherapy and to BCL2/BCL-XL inhibitors (van Delft et al, 2006; Wertz et al, 2011). These findings suggest that the inhibition of MCL1 is a novel and compelling therapeutic strategy for the treatment of malignancies.

2.2 Background

2.2.1 Disease

Myelodysplastic Syndromes (MDS) are malignant clonal disorders characterized by ineffective hematopoiesis; bone marrow dysplasia; peripheral cytopenias, including neutropenia, anemia, and/or thrombocytopenia; and a propensity to transform into acute myeloid leukemia (AML) (Albitar et al, 2002; Doll and List, 1989). The incidence of MDS in the United States is increasing, with approximately 20 000 to 30 000 new cases diagnosed annually and a median age of diagnosis approximately 70 years (Kadia et al, 2011; List 2005; Ma et al, 2007). By the International Prognostic Scoring System (IPSS) and Revised IPSS (IPSS-R), MDS patients are divided into two major risk groups: lower-risk and HR-MDS (Greenberg et al, 1997; Greenberg et al, 2012). Patients who

Protocol Number: 20200392

Date: 28 April 2022 Page 29 of 149

present to HR-MDS have a median OS of less than one year with best supportive care (Fenaux et al, 2009).

The selection of therapy for MDS is based on the patient IPSS risk category, age, and performance status. Treatment goals range from managing cytopenias and improving quality of life in lower-risk MDS to prolonging survival in HR- MDS (Cheson et al, 2006). Current treatment options for patients with MDS range from growth factor support or lenalidomide in low risk patients, to intensive chemotherapy and allogeneic hematopoietic stem cell transplantation (HSCT) for patients with high-risk disease. The use of lenalidomide has demonstrated significant clinical activity in patients with anemia and a chromosome 5q deletion (del [5q]), with response rates as high at 35% to 60% (Cheson et al, 2006). However, the only potentially curative therapy for MDS remains allogeneic HSCT. Yet, due to the high risk of HSCT-associated morbidity and mortality, less than 1000 patients with MDS currently undergo an HSCT in the US each year (Bejar and Steensma, 2014).

Therapeutic options for MDS remain limited despite some advances. A small percentage of patients with minimal comorbidities and good performance statuses are candidates for curative therapies, such as allogeneic stem cell transplantation. For the vast majority of patients, the lack of acceptable donors, advanced age, and/or serious comorbid medical conditions and organ dysfunction prevent access to curative options. For similar reasons, AML therapy-based intensive chemotherapy regimens present an unacceptable risk-benefit ratio for many patients. The Standard of Care (SOC) in MDS has generally been accepted as supportive in nature.

Over the past 15 years, clinical use of HMA, including azacitidine (Vidaza), have been shown to improve patient quality of life, decrease transfusion requirements, and improve outcome parameters in MDS patients and has become the SOC for patients with MDS requiring treatment (Fenaux et al, 2009; Kantarjian et al, 2006). Only azacitidine has demonstrated a survival advantage compared to conventional care regimens with best supportive care, low-dose cytarabine, or intensive chemotherapy with a median OS of 24.5 months versus 15.0 months respectively (Fenaux et al, 2009). However, not all patients respond to HMA therapy and, unfortunately, patients will ultimately progress on HMAs. Current research demonstrates overall response rate (ORR) of 28% to 48%, Complete Response rates of 6% to 34%, and median DOR of 8 to 10 months in all patients treated with HMAs (Kadia et al, 2011; Prebet et al, 2011). Patients who have failed HMA therapy have extremely poor prognoses with a median OS of 4 to 6 months

Protocol Number: 20200392

Date: 28 April 2022 Page 30 of 149

(Prebet et al, 2011; Jabbour et al, 2010). There are currently no Food and Drug Administration (FDA)-approved agents in the setting of HMA failure MDS patients, and there are limited therapeutic options, especially given the increased age and frequent comorbidities of this patient population. Because azacitidine is the only drug that has been shown to have a survival advantage for MDS patients, combination strategies with azacitidine-based therapy have become a major focus of clinical research (Steensma 2012).

2.2.2 Amgen Investigational Product Background: AMG 176

AMG 176 is a potent and selective inhibitor of protein-protein interactions between MCL1 (Myeloid Cell Leukemia Sequence 1) and pro-apoptotic members of the BCL2 family. Programmed cell death or apoptosis is regulated via a complex network of protein-protein interactions between the pro- and anti-apoptotic sub-groups that make-up the BCL2 protein family (Czabotar et al, 2014; Strasser et al, 2011; Kozopas et al, 1993). Myeloid cell leukemia sequence 1 is an anti-apoptotic member of this family and promotes cell survival. In contrast, pro-apoptotic family members such as BAK, BAX, or the BH3-only protein family members, such as BIM and PUMA, are critical effectors for the induction of apoptosis. Upon the induction of apoptotic stimuli, pro-apoptotic BH3 only proteins bind MCL1 and other pro-survival BCL2 family members, disrupting interactions between MCL1 and the pro-apoptotic effector proteins, BAK and BAX. This leads to activation and oligomerization of BAK and BAX, MOMP, and the release of cytochrome C, caspase activation and cell death (Czabotar et al, 2014; Strasser et al, 2011).

Malignant transformation results in cellular stress from a variety of pro-apoptotic insults, including hypoxia and gain-of-function mutations in oncogenes, suggesting there is a strong selective advantage for tumors to evolve mechanisms that culminate in the evasion of apoptosis. The over-expression of anti-apoptotic BCL2 family members, such as MCL1 and BCL2, has emerged as a central mechanism by which cancers buffer pro-apoptotic stress. There is now considerable data suggesting that MCL1 is integral to the resistance of apoptosis in a substantial number of solid and hematopoietic cancers. Genetic ablation of MCL1 has been shown to protect mice from the development of AML (Glaser et al, 2012). Additional mouse knockout studies have implicated MCL1 in the maintenance of plasma cells, an observation that suggests MCL1 may be a critical pro-survival factor in multiple myeloma (Peperzak et al, 2013). Myeloid cell leukemia sequence 1 is highly expressed in a variety of human tumors, and over-expression of

Protocol Number: 20200392

Date: 28 April 2022 Page 31 of 149

MCL1 has been implicated in resistance to chemotherapy and to BCL2/BCL-XL inhibitors (Wertz et al, 2011; van Delft et al, 2006). Finally, focal amplification of the MCL1 gene has been observed in up to 10% of cancers derived from multiple tissue types, including lung and breast (Beroukhim et al, 2010). These data suggest that the inhibition of MCL1 represents a novel and compelling therapeutic strategy for the treatment of cancer. A promising strategy for targeting MCL1 takes advantage of specific small molecules that selectively bind to MCL1 and disrupt its interactions with the BH3 domain of pro-apoptotic partner proteins such as BAK, and BIM, leading to the activation of the intrinsic apoptotic cascade and death in cells dependent on MCL1 for survival.

The MCL1 inhibitor AMG 176 is a first in class, small molecule therapeutic candidate with novel Mechanism of Action (MOA) (disruption of protein-protein interactions) with the potential to directly induce apoptosis in cells dependent on MCL1 for survival. Furthermore, the activity of AMG 176 in pre-clinical models suggests that AMG 176 may have utility in hematological malignancies, particularly MM and AML.

2.2.2.1 AMG 176 Preclinical Pharmacodynamic and Antitumor Studies

AMG 176 selectively disrupts the human MCL1:BIM interaction in a cell-free time resolved fluorescence resonance energy transfer-based assay with a mean inhibitory constant (Ki) of 0.00006 μmol/L (Caenepeel et al, 2018). Furthermore, AMG 176 is highly selective for MCL1, demonstrating > 4000-fold selectivity over the pro-survival BCL2 family members, BCL2 and BCL-XL in a BIM binding assay (Caenepeel et al, 2018). The profiling of a large and diverse panel of tumor cell lines revealed that AML cell lines were sensitive to MCL1 inhibition in vitro. This observation led us to test the hypothesis that the combinations of MCL1 inhibition with SOC agents may further sensitize AML tumors to treatment with an MCL1 inhibitor. We characterized the effects of MCL1 inhibition when combined with the BCL2 inhibitor venetoclax, cytarabine, decitabine, and doxorubicin in AML cell lines. A synergistic interaction was observed with all 4 combinations highlighting the potential for combining MCL1 inhibitors with SOC agents in AML (Caenepeel et al, 2018).

In vivo, treatment with AMG 176 significantly inhibited the growth of established orthotopic MOLM13-Luc AML tumors, at doses of 60 and 30 mg/kg on a 2 day on/5-day off (Every 2 Weeks [Q2W]) schedule (Caenepeel et al, 2018). The combination of AMG 176 and the HMA decitabine was also tested in the MOLM13 orthotopic AML xenograft model. Mice were treated with the combination of AMG 176 at 30 mg/kg

Protocol Number: 20200392

Date: 28 April 2022 Page 32 of 149

(Q2W) and decitabine administered 3 times a week at a dose of 1 mg/kg and activity compared against the single agent treatment. A significant reduction in tumor burden was observed with the combination of AMG 176 plus decitabine (98% tumor growth inhibition) compared to single agent AMG 176 (81% tumor growth inhibition) and single agent decitabine (64% tumor growth inhibition) (Caenepeel et al, 2018). We also tested the combination of AMG 176 and venetoclax in the MOLM13 orthotopic AML xenograft model. Mice harboring MOLM13 tumors were treated twice weekly with AMG 176 (30 mg/kg) and daily with venetoclax (50 mg/kg). Whereas both single agents achieved significant reductions in tumor burden (55% and 23%, respectively), the combination exhibited complete inhibition of tumor burden and achieved regression relative to the first day of dosing (Caenepeel et al, 2018). In summary, these data highlight the promise of AMG 176 as a novel therapeutic for the treatment of AML, and also illustrate the potential of AMG 176 to be combined with AML SOC to improve clinical outcomes.

2.2.2.2 AMG 176 Pharmacokinetics

AMG 176 was characterized in vitro and in vivo preclinical studies. In animal species AMG 176 had low drug Clearance (CL) relative to hepatic blood flow. In vitro, the metabolism of AMG 176 was catalyzed primarily by cytochrome P450 (CYP) 3A4 and CYP2C8.

In vitro, AMG 176 was highly bound to plasma proteins in all species including human (mean fraction unbound of 0.024) and did not partition into Red Blood Cells (RBCs), which makes plasma concentrations suitable for Pharmacokinetics (PK).

In vitro, AMG 176 was a non-selective CYP inhibitor in human liver microsomes (Ki ranged from 2.6 to 9.4 μ M, with the most potent effect against CYP2C9), a time-dependent inhibitor of CYP3A4 (Ki of 80 to 178 μ M and rate of enzyme inactivation [kinact] of 0.044 to 0.75 min⁻¹), an inducer of CYP2B6 and CYP3A4 in primary human hepatocytes, and an inhibitor of organic anion polypeptide transporters (OATP) 1B1, Breast Cancer Resistance Protein (BCRP), and OATP1B3 (concentration of drug producing 50% inhibition [IC50] of 1.2, 1.5, and 3.9 μ M, respectively). Subject to its administered dose and regimen, AMG 176 has the potential to cause CYP mediated Drug-Drug Interactions (DDIs) by inhibition (eg, inhibition of CYP3A4 substrates), CYP3A4 induction and transporter mediated DDIs.

Protocol Number: 20200392

Date: 28 April 2022 Page 33 of 149

2.2.2.3 AMG 176 Preclinical Toxicology

AMG 176 has been evaluated in a comprehensive series of toxicology studies in laboratory animals and in vitro test systems. The design of the nonclinical safety assessment program was in accordance with International Council for Harmonisation (ICH) Harmonised Tripartite Guideline S9, "Nonclinical Evaluation for Anticancer Pharmaceuticals" (ICH S9, 2010). The goal of this program was to adequately characterize the toxicity of AMG 176 for clinical use.

Potency of AMG 176 vs MCL1 interaction in the dog is nearly identical to that seen in the human. The potency of AMG 176 vs the rodent MCL1 protein is 177-fold lower than in the dog (AMG 176 Investigator's Brochure [IB]). AMG 176 nonclinical safety studies consisted of an exploratory 14-day dog Intravenous (IV) toxicology study, Good Laboratory Practices (GLP) 28-day rat and dog IV toxicology studies, in vitro and in vivo phototoxicity assay, an in vitro hemolysis assay, and in vitro safety pharmacology studies (human ether-à-go-go-related gene [hERG] and isolated rabbit heart) to characterize potential cardiovascular effects (AMG 176 IB).

The doses selected for the 28-day IV dog and rat toxicology studies were intended to characterize the toxicity of AMG 176 and provide data to support a starting dose for the First-In-Human (FIH) study. An IV route of administration and a dosing schedule of 2 days of dosing followed by 5 days of non-dosing was used to support the anticipated clinical route and dosing schedule. While no preclinical safety data exist for Once Weekly (QW) dosing, the twice weekly dosing data provide a conservative case and no additional safety concerns are anticipated with QW dosing. In a 28-day rat IV infusion toxicology study the severely-toxic dose in 10% of the animals (STD10) was 60 mg/kg based on mortality at 120 mg/kg and in a 28-day IV toxicology study in dogs, the Highest-Non-Severely-Toxic Dose (HNSTD) was 10 mg/kg based on early deaths at 20 mg/kg. In both the rat and dog, morbidity and mortality were related to mucosal epithelial degeneration in the small and large intestines. AMG 176 was phototoxic in an in vitro assay but not in an in vivo study, the latter of which is considered definitive. AMG 176 in vehicles containing hydroxypropyl-β-cyclodextrin caused hemolysis of whole blood at concentrations of 0.048, 0.12, 0.24, 1.2, and 2.4 mg/mL in rat blood and at 0.1 and 1.0 mg/mL dog blood.

2.2.2.4 AMG 176 Clinical Experience

AMG 176 is currently being investigated in 2 ongoing clinical studies: Study 20150161, a phase 1, FIH, multicenter, nonrandomized, open-label, dose-exploration study in

Protocol Number: 20200392

Date: 28 April 2022 Page 34 of 149

subjects with R/R multiple myeloma and in subjects with R/R AML; and Study M16-785, a phase 1b study of venetoclax and AMG 176 in patients with R/R hematologic malignancies.

A phase 1, FIH study of AMG 176 (Study 20150161) is ongoing. As of 15 June 2021, preliminary data were available for 48 subjects with MM who had received at least 1 dose of AMG 176:

- Thirty-six subjects in Part 1a (once daily for two consecutive days [QD2] dosing schedule)
 - In Part 1a:
 - o Four subjects in the 50 mg/m² cohort;
 - o Three subjects each in the 30, 40, 60, and 120 mg/m² cohorts,
 - o Two subjects in the 240 mg/m² cohort,
 - Four subjects each in the 120/180 mg/m² and 120/240 mg/m² cohorts, and
 - Five subjects each in the 120/360 mg/m² and 120/480 mg/m² cohorts.
- Twelve subjects in Part 1b (QW dosing schedule)
 - In Part 1b, 3 subjects each in 120/180, 120/240, 120/360, and 120/480 mg/m² cohorts.

Preliminary data were also available for 37 subjects with AML who had received at least 1 dose of AMG 176 (see also Section 2.3.1 for efficacy data):

- Fifteen subjects in Part 3a (QD2 dosing schedule)
 - In Part 3a, 5 subjects each treated in the 60, 120, and 120/180 mg/m² cohorts.
- Two subjects in Part 3 QW Japan (a dose cohort described in a country-specific supplement)
 - In Part 3 QW Japan, 2 subjects were in 120/180 mg/m² cohort
- Eight subjects in Part 3b (QW dosing schedule monotherapy at 120 mg/m²)
- Four subjects in Part 3c (QW dosing schedule monotherapy at 120 mg/m² in Japan)
- Eight subjects in Part 4 (QW dosing schedule in combination at 60 mg/m² with azacitidine).

Since the safety cutoff, 5 Dose Level Review Meetings (DLRMs) have been held on Study 20150161 at the 120 mg/m² and 180 mg/m² monotherapy doses (Part 3b) and the 60 mg/m² and 120 mg/m² combination doses (Part 4); no concerning safety events (including elevations of troponin) and no DLTs were observed. Evaluation of the Part 4 180 mg/m² combination will be completed and results reviewed prior to opening enrollment at that dose level on this study.

A detailed description of the chemistry, pharmacology, PK, efficacy, and safety of AMG 176 is provided in the Investigator's Brochure.

Protocol Number: 20200392

Date: 28 April 2022 Page 35 of 149

2.2.3 Non-Amgen Non-Investigational Product Background: Azacitidine

2.2.3.1 Azacitidine Pharmacokinetics

The pharmacokinetics of azacitidine were studied following a single 75 mg/m² Subcutaneous (SC) dose and a single 75 mg/m² IV dose. Azacitidine is rapidly absorbed after SC administration, with peak plasma concentrations achieved in 0.5 hour. Mean half-life ($t_{1/2}$) after SC administration is 41 \pm 8 minutes.

Urinary excretion is the primary route of elimination of azacitidine and its metabolites. In vitro studies indicate azacitidine may be metabolized in the liver. No formal clinical DDI studies with azacitidine have been conducted. In vitro studies indicate that azacitidine did not cause any inhibition of CYP2B6 and CYP2C8 or induction of CYP1A2, CYP2C19 or CYP3A4/5. Refer to the United States Prescribing Information (USPI) for additional information.

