| Cardiac monitoring tests ^j | Х | Χ | | | | | | | | | | Χ | | Χ | | Х | | | | | | | Χ | | Χ | Χ | | | Χ | Χ | Χ | | | Χ | Χ |
| Pregnancy test ^k | Х | Х | | | | | | | | | | | | | | | | | | | | | | | | | | | | | | | | | |
| Hepatitis serology | Х | | | | | | | | | | | | | | | | | | | | | | | | | | | | | | | | | | |
| | | | | | | | | | | | | | | | | | | | | | | | | | | | | | | | | | Page | e 1 d | of 2 |

Protocol Number: 20200392

Date: 28 April 2022 Page 23 of 149

Table 1-3. Schedule of Activities: Part 1B and Part 2, Combination Therapy Cycle 1, All Doses

| | Screen | | | | | | | | | | | | | | | | | Tre | eatn | nent | t | | | | | | | | | | | | | | |
|--|----------------|----------|-----|-----------|-----|---|---|---|---|---|---|---|----|--------------|--------|----------|---|-----|------|------|---|---|---|----|--------------|----------|---|-----|---|---------------|----------|---|-----|------|---------------|
| Cycle | | | | | | | | | | | | | | | | | | | 1 | | | | | | | | | | | | | | | | |
| Days | -14 to 0 | | | | | | 1 | | | | | | | 2 | 3 to 7 | | | | | 8 | | | | | 9 | | 1 | 5 | | 16 | | 2 | 2 | | 23 |
| Hours (relative to start of dosing) | | Pre-dose | 0 | 5 minutes | EOI | _ | 2 | ω | 4 | 5 | 7 | 8 | 12 | 24h after D1 | | Pre-dose | 0 | EOI | ω | 4 | 5 | 7 | 8 | 12 | 24h after D8 | Pre-dose | 0 | EOI | 8 | 24h after D15 | Pre-dose | 0 | EOI | 8 | 24h after D22 |
| Local labs (continued) | • | | | | | | | | | | | | | | | | | | | | | | | | | | | | | | | | | | |
| HIV testing ^l | Х | | | | | | | | | | | | | | | | | | | | | | | | | | | | | | | | | | |
| Central labs | | | | | | | | | | | | | | | | | | | | | | | | | | | | | | | | | | | |
| AMG 176 PK ^{m,n} | | Х | | | Х | | | Х | | Х | Х | Х | | Х | | Х | | Х | Χ | | Х | Х | Х | Х | Х | Х | | Х | Х | Х | Χ | | Х | Χ | Χ |
| Azacitidine PK ^{m,o} | | Х | | Х | Х | Х | Х | | Х | | | Х | | | | | | | | | | | | | | | | | | | | | | | |
| DISEASE AND IMAGING A | SSESSI | MEI | NTS | 3 | | | | | | | | | | | | | | | | | | | | | | | | | | | | | | | |
| Bone marrow aspirate/biopsy ^p | Х | | | | | | | | | | | | | | | | | | | | | | | | | | | | | | | | | | |
| Peripheral blood count | Х | Х | | | | | | | | | | | | | | Х | | | | | | | | | | Χ | | | | | Χ | | | | 1 |
| | | | | | | | | | | | | | | | | | | | | | | | | | | | | | | | | | | | |
| 0 | | | | | | | | | | | | | | | | | | | | | | | | | | | | | | | | | Paç | ge 2 | of 2 |

Protocol Number: 20200392

Date: 28 April 2022 Page 24 of 149

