6.1.2 Non-investigational Products

The non-investigational product used in this study (azacitidine) may be considered investigational in some countries. Refer to regional prescribing information for full details.

Decisions regarding the AMG 176 lead-in dosing period regimen, lead-in period starting dose, dosing increments, will be made by DLRT and communicated to the IRB/IEC, as appropriate (see Section 11.3).

Azacitidine will be administered at 75 mg/m² IV over approximately 15 minutes or via subcutaneous injection daily for 7 days on days 1 to 7 of each treatment cycle. Treatment cycles will begin on day 1 of each new azacitidine cycle.

Azacitidine will be dosed based on actual body weight. However, at the treating physician's discretion, an adjusted body weight may be used, if the actual body weight is greater than 40% over the ideal body weight.

 $Adjusted\ body\ weight \\ = 0.4(actual\ body\ weight-ideal\ body\ weight) + ideal\ body\ weight$

The patient's baseline body weight will be used throughout treatment with consideration given to update the dosing weight for a weight change of greater than 10%.

After cycle 1, azacitidine may be subsequently administered at any of the Houston Area Locations (HALs) or at the patients' local oncologists' offices, and a schedule of 7 azacitidine doses within 9 days is allowed due to possible weekend closure of local offices. Patients will receive one course every 4 to 8 weeks; however, delays of more than 8 weeks may be allowed if determined by the investigator to be in the best interest of the patient after discussion with the PI and the discussion documented in the patient's medical record.

Azacitidine will be obtained from commercial sources. Please refer to the FDA prescribing information for azacitidine for further details.

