9.4.2.4 Other Analyses

9.4.2.4.1 Pharmacokinetic Analyses

The analysis of pharmacokinetic endpoints will include data from all subjects who have received at least 1 dose of the investigational product and have at least 1 pharmacokinetic sample collected.

Pharmacokinetic parameters for AMG 176 and azacitidine including, but not limited to, maximum observed concentration (C_{max}), minimum observed concentration (C_{min}), Area Under the plasma Concentration time curve (AUC), CL, and, if feasible, $t_{1/2}$ will be estimated using standard noncompartmental PK methods and summarized by dose groups using means, standard deviations, medians, minimums, and maximums for intensive and peak/trough determinations. Concentrations at each time point along with PK parameter values may be reviewed for each subject. Individual concentration-time profiles will be plotted by dose groups. Summary statistics will be computed for each sampling time and parameter as appropriate. Analysis of the relationship between AMG 176 dose and exposure parameters (AUC and C_{max}) will be conducted and plots of the relationship between AMG 176 dose and exposure parameters along with dose proportionality assessment will be provided, if feasible. Additional analyses to explore relationship between exposure and safety and exposure and efficacy may also be performed.

Protocol Number: 20200392

Date: 28 April 2022 Page 90 of 149

10. References

AMG 176 Investigator's Brochure. Thousand Oaks, CA. Amgen Inc.

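### For subcutaneous azacitidine the PK schedule has no sample at the protocol's own stated 0.5 h peak, and the EOI draw is undefined, so SC Cmax is biased low and not comparable with IV

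*Protocol*

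**What the plan says.** Protocol section 2.2.3.1 gives the SC peak: "Azacitidine is rapidly absorbed after SC administration, with peak plasma concentrations achieved in 0.5 hour". The same paragraph puts the mean SC half-life at 41 ± 8 minutes.

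Section 6.1.2 allows two routes at 75 mg/m²: "IV over approximately 15 minutes or via subcutaneous injection daily for 7 days".

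In Table 1-3 (Part 1B and Part 2, cycle 1), the "Azacitidine PK" row is marked at pre-dose, 5 minutes, EOI, 1, 2, 4 and 8 h on day 1. The table has no 0.5 h column. Footnote o sets the clock: "All azacitidine timepoints are relative to azacitidine administration". Footnote m sets the tolerance after dosing: "PK samples should be collected within ± 15 min of the designated time points". It also asks for collection at the exact nominal time and for actual dose and sample times to be documented.

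Azacitidine Cmax, AUC, CL and half-life are secondary endpoints of Parts 1B and 2 (Protocol section 3). Section 9.4.2.4.1 takes Cmax as the maximum observed concentration, uses noncompartmental methods, and has the parameters "summarized by dose groups using means, standard deviations, medians, minimums, and maximums". It does not mention route.

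**The concern.** EOI has a meaning only for an infusion, and neither the table nor its footnotes give an SC equivalent. If no EOI sample is drawn after an injection, the SC profile jumps from 5 min to 1 h and the stated peak falls in the gap. Noncompartmental Cmax is the highest value seen, so nothing in the analysis recovers a peak that was not sampled.

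The bias depends on route. Read with footnote o, an IV subject has a draw at the end of the 15-minute infusion, where the concentration is highest. An SC subject has no counterpart. With at most 10 subjects per Part 1 cohort and no split by route, the IV/SC mix of a cohort can shift its mean azacitidine Cmax for reasons unrelated to exposure.

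**Working it through.** **1. Does any sampling window contain 30 min?** Each nominal time ± 15 min:

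| Nominal time | Window (min) | Contains 30 min? |
|---|---|---|
| 5 min | −10 to 20 | no |
| EOI, if read as 15 min | 0 to 30 | only at its last minute |
| 1 h | 45 to 75 | no |
| 2 h | 105 to 135 | no |

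The 5-minute window opens 10 minutes before the dose. If EOI instead means the end of the 2-hour AMG 176 infusion, and both drugs start together, it coincides with the existing 2 h draw and does not help.

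**2. How low would the observed SC peak be?** The protocol gives only the 0.5 h peak and the 41 ± 8 min half-life. The model is an assumption: one compartment with first-order absorption and elimination, C(t) ∝ exp(−ke·t) − exp(−ka·t).

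- ke = ln 2 / 41 = 0.0169 per min.
- ka is solved from ln(ka/ke)/(ka − ke) = 30 min, giving ka = 0.0580 per min.
- At 30 min: 0.602 − 0.176 = 0.427 (rounded from unrounded terms).
- At 60 min: 0.363 − 0.031 = 0.332, and 0.332/0.427 = 0.78.
- At 15 min: 0.776 − 0.419 = 0.357, and 0.357/0.427 = 0.84.

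Concentration as a fraction of the true SC peak:

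| Half-life | 5 min | 15 min | 20 min | 45 min | 1 h | 2 h |
|---|---|---|---|---|---|---|
| 33 min | 0.39 | 0.83 | 0.93 | 0.92 | 0.76 | 0.25 |
| 41 min | 0.40 | 0.84 | 0.94 | 0.92 | 0.78 | 0.31 |
| 49 min | 0.41 | 0.84 | 0.94 | 0.93 | 0.80 | 0.36 |

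At nominal times with no EOI sample, the highest value is the 1 h sample, 0.76 to 0.80 of the peak, so Cmax is 20 to 24% low. With a 15-minute sample the highest value is 0.83 to 0.84, so Cmax is 16 to 17% low. At 8 h, 480/41 = 11.7 half-lives after the dose, the level is about 0.1% of the peak.

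**3. What happens to AUC?** The integration rule is not specified, and it matters. Results at a half-life of 41 min, relative to the true AUC:

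| SC samples after dose | Linear trapezoid | Linear-up/log-down |
|---|---|---|
| 5 min, 1, 2, 4, 8 h | 0.93 (7% low) | 0.83 (17% low) |
| plus 15 min | 1.04 (4% high) | 0.94 (6% low) |
| plus 30 min | 1.05 (5% high) | 0.95 (5% low) |

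With no EOI sample, both rules give a low AUC, but by amounts that differ by 10 percentage points. AUC is therefore a less certain problem than Cmax.

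**The case against.** **Cmax is still derivable.** A reader might infer that SC Cmax cannot be obtained at all. That is not so: it is defined as the maximum observed concentration, and any SC subject with samples has one. The fault is bias and lack of comparability. This part of the objection stands in full.

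**The window is a tolerance, not a target.** Footnote m asks for the exact nominal time and for actual times to be recorded. Analysis on actual times removes most of the labelling error. Off-nominal draws can even fall nearer the peak (0.94 at 20 min, 0.92 at 45 min). This stands, but actual times do not supply a sample at 30 min, and a post-dose window that opens before the dose is still a drafting fault.

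**A false AMG 176 effect is not a planned inference.** A reader might also infer that the plan would report a spurious effect of AMG 176 on azacitidine exposure. The documents do not go that far. The dose–exposure analysis in section 9.4.2.4.1 concerns AMG 176 exposure, there is no azacitidine-alone arm, and section 2.3.2 calls an interaction unlikely. What remains is that the descriptive summaries mix routes, and their wording does not forbid a split.

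**Details may be elsewhere.** Section 8.5 refers to a separate laboratory manual, which may define an SC time for the EOI draw. It is not available here. The documents also do not say how many subjects received SC dosing.

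**The consequences for this trial are small.** SAP section 3.1 records that Part 2 did not enroll, and SAP section 9.7.1.1.1 estimates parameters for AMG 176 only. This stands. However, SAP section 2.1 still lists azacitidine PK as an endpoint, and SAP section 10 does not record it as dropped.

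**Conclusion.** The point holds as a design inconsistency. The protocol states an SC peak at 0.5 h and then schedules no SC sample there, and the one draw that could have covered it is defined only for an infusion. This follows from the text alone.

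The size rests on an assumed one-compartment model with its peak at 30 min and a half-life of 33 to 49 min. SC Cmax is about 20 to 24% low if no EOI sample is drawn, or about 16 to 17% low if EOI is taken as 15 min. SC Tmax is missed as well. With no EOI sample, AUC is about 7% low by linear trapezoid and about 17% low by linear-up/log-down, so no single AUC figure should be quoted.

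The documents do not show that any reported result of this trial is wrong on this account. The matter bears mainly on the design and on how any azacitidine concentrations are presented.

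**What to change.** 1. **Table 1-3 and footnote o:** state that for SC dosing the EOI sample is drawn 30 min after injection, and that for IV dosing EOI means the end of the azacitidine infusion. The number of draws is unchanged. The 8 h sample carries almost no azacitidine information but need not be moved.
2. **Footnote m:** give the early azacitidine samples a window narrower than ±15 min, so that the 5-minute sample cannot precede the dose. State that the noncompartmental analysis uses actual times.
3. **Section 9.4.2.4.1:** summarise azacitidine PK separately for IV and SC, and name the AUC integration rule.
4. **For this trial's report:** show any azacitidine data by route, on actual times, and say that the SC peak was not sampled. Record in SAP section 10 that azacitidine PK parameters are not estimated, if that is the intention.

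Cost: amendment wording, one draw at a separate clock time on a day when subjects are already in hospital, and smaller summary groups. In the model, a 30-minute sample captures the peak by construction, and AUC then lies within about 5% of the true value under either integration rule (half-life 41 min).
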